**** Protocol:**

Prophylaxis: Administer gammaCore® Sapphire daily, prophylactically, scheduled three times a day (morning, mid-day and 1 hour before bed at night). One treatment is defined as 2 consecutive doses (stimulations). Each dose delivers a 2-minute stimulation. One dose is applied to the left side of the neck, then one is applied to the right. This would be a total of 6 treatments (2 stimulations x 3 times per day).

For acute respiratory distress or shortness of breath (SOB): Administer one treatment of gammaCore® for acute treatment of shortness of breath (as needed, up to nine times a day). One treatment is defined as 2 consecutive doses (stimulations). Each dose delivers a 2-minute stimulation. One dose (stimulation) is applied to the left side of the neck, then one to the right. If shortness of breath (SOB) persists 20 minutes after start of first treatment, administer a second treatment. If the additional treatments do not appear to be providing benefit/relief of symptoms (as per patient or physician discretion) there is no need to continue with additional acute treatments. However, if it there appears to be benefit, the patient can administer more as needed. The patients can receive up to 9 acute treatments (or 18 stimulations) per day.

Determination of benefit/relief of symptoms will be determined collaboratively between patient and a research investigator who is caring for the patient. Should the acute treatments not provide any relief, the research investigator will determine if/what standard of care therapies are necessary, to treat symptoms. If patient remains in stable condition, they can continue with prophylactic treatments (3xday), when/if possible. Once symptoms are treated (standard of care) and patient is stable again, they can resume the acute treatments (up to 9x day) and continue with this process, until study completion (until they are placed on mechanical ventilation, are discharged, or can no longer continue with treatments, per patient or physician discretion/withdrawal from study).

The devices are pre-programmed to not allow more than 30 stimulations in a 24 hour period. This is a safeguard with the device that cannot be changed. Once the maximum daily number of treatments has been reached, the device will not deliver any more stimulations until the following 24-hour period. (The stimulation automatically stops 120 seconds after the device is powered on).

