7.2.1.5 Day of Study Completion

The last day of the study will be determined by discharge, transition to mechanical ventilation and/or if the patient is unable to continue. The following will be recorded:

- Study Measurements
 - Height/Wt, BMI
 - Temperature
 - Blood Pressure
 - O₂ Saturation
 - PaO₂/FiO₂ ratio
 - Shortness of Breath (Yes / No)
 - Cough (Yes / No)
- Labs
 - Pro-Calcitonin
 - C-reactive protein

Clinical Investigation Plan

- Ferritin
- D Dimer
- CBC with differential
- Comprehensive metabolic panel
- nVNS stimulations
 - Total number of gammaCore® treatments administered
 - Date and time of stimulations
- Daily Tx Log
 - Oxygen Required (Yes / No)
 - Oxygen level (%) based on device type (HFNC / NC / Bipap / Optiflow)
 - Ventilator Dependence (Yes / No)
 - Date and time of Ventilation
 - Patient discharge home (Yes / No)
 - Date and time (in 24 hour format) of Discharge
 - Survival (Yes / No) with Date and Time of Death
- Clinical Improvement Scale
 - Concomitant medication assessment
 - Adverse event assessment

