7.4.4 Removal of Patients from the Clinical Investigation

Patients are free to discontinue participation in the investigation at any time, without prejudice to further treatment. Patients who discontinue the investigation should always be asked about the reason(s) for their discontinuation and about the presence of any adverse event (AE)/adverse device effect (ADE) and, if possible, be assessed by a Clinical Investigator.

Patients may be withdrawn from investigation treatment and assessments at any time, if deemed necessary by the Clinical Investigator.

Specific reasons for withdrawal of patients from this investigation are:

- The decision of a patient to withdraw from the investigation (including if the patient withdraws informed consent)
- Unacceptable adverse event
- Patient lost to follow-up; or
- Patient is non-compliant with study procedure

In case of withdrawal, AEs/ADEs should be followed up.

Incorrectly enrolled patients will be withdrawn from further investigation and assessments. A protocol deviation will be submitted to the IRB via a prompt report form.

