7.8.4 Reporting of Adverse Events/Adverse Device Effects

7.8.4.1 Methods for Eliciting Adverse Events/Adverse Device Effects

All patients will be carefully monitored for the occurrence of AEs during the investigation period from the run-in to the completion of follow up. The Clinical Investigator will collect AE information using non-leading questions such as "have you experienced any new health problems or worsening of existing conditions". Events directly observed or spontaneously volunteered by patients will also be recorded.

Clearly related signs, symptoms and abnormal diagnostic procedure results should be grouped together and reported as a single diagnosis or syndrome whenever possible.

All AEs including but not limited to events reported by the patient or reported in response to an open question by the Clinical Investigator or member of this team, which fall into any of the above definitions must be recorded as an AE in the CRF and should include the following information.

- Brief description of the event (diagnosis)
- Start date (and time, if relevant)
- Stop date (and time, if relevant) (or resolution)
- Severity
- Action taken regarding the medical device
- Opinion on causality
- Seriousness
- Outcome

Severity

Severity describes the intensity of an event and will be assessed as:

Mild

The AE does not interfere in a significant manner with the patient's normal functioning level. It may be an annoyance.

Moderate

The AE produces some impairment of function but not hazardous to health. It is uncomfortable and/or an embarrassment.

Severe

The AE produces significant impairment of functioning or incapacitation and/or it is a hazard to the patient.

If an AE changes in severity, it should be reported as an AE of new severity but with the same description.

Causality (Adverse Device Effects/ADE)

Causality will be assessed as:

- Related (definitely, possible or probable) - A causal relationship between the clinical investigational medical device and the AE is at least a reasonable possibility, i.e. there is evidence or argument suggesting a causal relationship.
- Not related - There is no indication that the AE was caused by the clinical investigational medical device.

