7.8.4.2 Follow-up of Patients with Adverse Events

Any AE that is ongoing when the patient is withdrawn from the investigation should be followed-up until the AE is resolved or the Clinical Investigator decides that the AE is stable and needs no further follow-up. The date when the Clinical Investigator considers one of these outcomes to have occurred for the last ongoing AE for a patient will be considered the last visit for this patient, and the outcome should be recorded in the CRF.

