7.8.5 Reporting of Events

INTERNAL: REPORTABLE EVENTS THAT OCCUR AT THE PI's RESEARCH SITE or are ASSOCIATED WITH THE PI			
Event	Examples (not all-inclusive)	How to Report	Report Timeframe
Serious Adverse Event (SAE)	
 ◦ Pneumonia resulting from study drug administration ◦ Significant allergic reaction resulting from study drug(s) ◦ Cardiovascular event induced by study drug(s) 	Prompt Report Form Copy of SAE Report to Sponsor Copy of subject's signed ICF	5 days
Unanticipated Adverse Device Event (UADE)	
 ◦ Guide wire breaks during insertion and cannot be retrieved ◦ Revision surgery to replace component ◦ Cardiovascular event induced by study device 	Prompt Report Form Copy of UADE (Device SAE) Report to Sponsor Copy of subject's signed ICF	5 days
SAE or UADE resulting in death	
 ◦ Any death related or possibly related to use of investigational drug or device 	Prompt Report Form Copy of SAE Report to Sponsor Copy of subject's signed ICF	24 hour phone notice 5 days: written report
Deaths within 30 days of study treatment (all others reported at continuing review)	
 ◦ Any death that occurs within 30 days of receiving study drug/device/intervention, regardless if PI determined death is "unrelated" and/or "expected" (this excludes MINIMAL RISK STUDIES such as registries or observational studies). 	Prompt Report Form Copy of SAE Report to Sponsor	5 days
Major Protocol Deviation/ Violation	
 ◦ Failure to obtain informed consent ◦ Omitting study procedure(s) required by-approved protocol ◦ Drug dispensing/dosing error ◦ Failure to securely control the study product ◦ Deviation necessary to eliminate an apparent immediate hazard to a participant 	Prompt Report Form	5 days
Research Complaint	
 ◦ Complaint from a participant regarding a research-related injury or study activities ◦ Complaint from study personnel regarding fabrication of data or research misconduct 	Prompt Report Form	5 days

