7.10.1.6 Adverse Events/Adverse Device Effects

Device-related serious adverse events will be tabulated. The overall incidence of device-related serious adverse events will be summarized and presented as a proportion and respective 95% exact binomial confidence interval. Additionally, an overview of events, to include total numbers of events, and total number of subjects with events will be tabulated and presented for all AEs, serious AEs, and device-related AEs and device-related serious AEs, as well as deaths. Events will be presented overall and by study arm.

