7.12 Deviations from the Clinical Investigation Plan

Every effort should be made to comply with the requirements of the protocol. If the changes or deviations may affect the rights, safety, or welfare of participants, IRB/IEC approval is required. Deviations will be recorded with an explanation for the change. Corrective action will be implemented to avoid repeat deviations.

The reasons for any patient's withdrawal and discontinuation from the investigation will be recorded. If such discontinuation is because of problems of safety or lack of effectiveness, the patient will still be followed up in the investigation, if possible.

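### The safety windows do not fit the planned exits or the control arm: no follow-up rule for adverse events open at discharge or ventilation, and no common clock for 30-day deaths

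*Combined protocol and SAP*

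**What the plan says.** **End of participation.** Section 7.2.1.5 states: "The last day of the study will be determined by discharge, transition to mechanical ventilation and/or if the patient is unable to continue". The synopsis and footnote e of Table 1 agree. The treatment note in section 7.2.1.1 lists the routes out one by one: treatment continues "until they are placed on mechanical ventilation, are discharged, or can no longer continue with treatments, per patient or physician discretion/withdrawal from study".

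**Follow-up of open adverse events.** Section 7.8.4.2: "Any AE that is ongoing when the patient is withdrawn from the investigation should be followed-up until the AE is resolved", or until the investigator judges it stable. Section 7.4.4: "In case of withdrawal, AEs/ADEs should be followed up". Section 7.12 adds a limited extension, where possible: "If such discontinuation is because of problems of safety or lack of effectiveness, the patient will still be followed up".

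**Adverse event window.** Section 7.8.4.1 monitors all patients "from the run-in to the completion of follow up".

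**Late deaths.** One row of the IRB reporting table in section 7.8.5 requires a report within 5 days of "Any death that occurs within 30 days of receiving study drug/device/intervention", whether or not the death is thought related or expected. Other deaths are left to continuing review.

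**Analysis.** Section 7.10.1.6 tabulates adverse events, serious adverse events, their device-related subsets and deaths: "Events will be presented overall and by study arm".

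**The concern.** The follow-up duty is attached to the exceptional exit and not to the expected ones. A patient who withdraws with an open event has a rule. A patient who is discharged or ventilated with the same event has none. Ventilation matters most here, because a patient leaving for that reason may well have a serious event unresolved on the day of exit.

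The 30-day death row is the only provision that clearly reaches past the end of participation without regard to cause. Its clock depends on receiving something that controls do not receive, and the visit schedule contains nothing that would bring such a death to the trial team's notice.

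Demonstrating safety is a stated aim (sections 6 and 7.7.2), mortality is a listed clinical event, and deaths are shown by arm. Allocation is open, since the control is standard of care without a sham. A reporting trigger that depends on the arm is a poor basis for a by-arm death table, even a descriptive one.

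**Working it through.** The plan states no figure on this point, so the check sets the provisions side by side.

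1. **Exit route against follow-up rule for an open adverse event.**
   - Withdrawal: covered by 7.4.4 and 7.8.4.2.
   - Discontinuation for safety or lack of effectiveness: covered by 7.12, if possible.
   - Discharge: no rule stated.
   - Transition to mechanical ventilation: no rule stated.

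   The list in section 7.2.1.1 names discharge and ventilation separately from withdrawal, so they cannot simply be read as forms of it.

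2. **Ends of the adverse event window.** Section 7.2 and Table 1 go from admission (Day 0) through the hospital days to study termination. There is no run-in before Day 0 and no visit after termination. Both ends of the window in 7.8.4.1 therefore point to periods that the trial does not define. Its coverage of all patients cannot fill the gap in step 1, because its closing date is unknown.

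3. **Start of the 30-day death clock.**
   - Control arm: the synopsis states that standard-of-care patients are not given the device. If intervention is read broadly enough to include standard of care, there is still no start date.
   - Device arm: treatment is repeated daily until exit, and the row does not say whether first or last use starts the count.

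4. **Means of meeting the duty.** Survival is recorded in the daily log up to and including the completion day. Nothing is scheduled later in either arm. A death after discharge, or after a patient leaves the study on a ventilator, comes to light only by chance or through routine records.

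5. **Other routes for a death.** Under 7.8.2 death makes an adverse event serious and reportable to the IRB, with no restriction by arm, and the serious adverse event row in 7.8.5 gives 5 days. This works during the study. After exit it is weaker:
   - 7.8.1 ties an adverse event to the time of participation.
   - Every example in the serious adverse event row is caused by treatment.
   - 7.10.4 records that one serious adverse event unrelated to the device was not reportable.

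6. **Size.** The effect on the death table depends on the post-exit death rate and on the share captured in each arm. The documents give neither. Section 7.4.1 plans up to 30 patients per arm, so a single death moves an arm's proportion by 1/30, about 3.3 percentage points. That shows how coarse the table is; it does not estimate bias.

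**The case against.** The strongest reply is that section 7.8.5 is an institutional reporting table. It sets how quickly a known death goes to the IRB, not which deaths are looked for or tabulated, and section 7.10.1.6 does not refer to it. Control deaths in the study are serious adverse events, and survival is logged daily and at completion in both arms. The primary safety measure is treatment-related serious adverse events (7.7.3), and by-arm comparisons are declared nominal (7.10.1.2). All of this stands, and it limits the point.

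Two stronger readings are tempting. A reader might infer that late deaths will be sought in device patients and missed in controls, giving a spurious excess against the device. The documents do not support that. No contact after exit is planned in either arm, so similar under-capture in both is at least as plausible, and no rate is given from which to size a difference.

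A reader might also infer that events open at discharge are discarded. The plan is silent; it does not say to stop following them. Adverse events are assessed on the completion day, and outcome is a required item in the case report form. An event open at discharge may lack a stop date, but its status on that day is still to be recorded.

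The reply does not supply a follow-up rule for the two planned exits, a defined end to the adverse event window, or any scheduled means of learning of a death up to 30 days.

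**Conclusion.** The point holds as a mismatch between the safety provisions and the trial they serve. Adverse events open at discharge or ventilation have no stated follow-up rule. The adverse event window names periods that do not exist. The 30-day death row has no start date for controls, an ambiguous one for the device arm, and no scheduled contact behind it in either arm, so it cannot be met reliably.

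Unequal capture of post-exit deaths by arm is a risk, not a demonstrated bias. It would arise only if the reporting row led staff to pursue late deaths more actively in device patients, which the documents neither require nor prevent. Its size cannot be computed from what they give. The conclusion assumes that withdrawal excludes discharge and ventilation, as the list in section 7.2.1.1 indicates. The change should be made, because safety is a stated aim and the repair is small.

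**What to change.** Define one safety and vital-status window for both arms, from randomisation to a common date, for example Day 30, whatever the reason for leaving the study.

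- **7.8.4.1:** replace the run-in and follow-up wording with that window.
- **7.8.4.2:** apply the follow-up rule for ongoing adverse events to every exit, naming discharge and mechanical ventilation. Align 7.4.4 and 7.12 with it.
- **7.8.5:** leave the institutional IRB row as it is.
- **7.10.1.6:** base the death tabulation on the common window in both arms, so that it does not depend on the IRB clock.
- **Table 1:** add one chart check or telephone call at the common date, identical in both arms, recording vital status and the status of open adverse events.

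The cost is a wording amendment, one brief contact for up to 60 patients (30 per arm, section 7.4.1) and slightly later database closure. Treatment is unchanged.

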7.8.6 Device deficiencies

All device deficiencies related to the identity, quality, durability, reliability, safety or performance of an investigational medical device shall be documented on a separate DD form and provided to IRB via prompt report and electroCore within 24 hours of the event.

7.9 Data Quality Assurance

7.9.1 Monitoring, Audits and Inspections

During the investigation, the PI will be responsible for the monitoring of the clinical trial to ensure the research team is following all aspects of the CIP. All data must be accurately recorded in the CRF. Source data verification (a comparison of data in the CRF with the patient's medical records and other records at the investigation site) with access to records may also be performed by the institution's Quality Coordinator.

Authorized representatives of Regulatory agencies may visit the site to perform audits or inspections, including source data verification.

7.9.2 Patient Records and Source Data

Data may be recorded directly in the CRF, which will then be considered as source data. It is the responsibility of the Clinical Investigator to record essential information in the medical records in accordance with national regulations and requirements, including:

- Investigation code
- Patient screening number and/or patient number
- That informed consent for participating in the study was obtained
- Diagnosis
- All data entry days during the investigation period
- All AEs/ADEs
- Treatments
- The SN number of the device

The Clinical Investigator is responsible for ensuring the accuracy, completeness, legibility and timeliness of the data recorded in the CRFs. Signed CRFs will be collected and monitored on a regular basis.

7.9.3 Access to Source Data and Documentation

The Clinical Investigator should guarantee access to source documents for the Quality Coordinator and auditors as well as for inspection by appropriate regulatory agencies, and the IRB/IEC, if required.

7.9.4 Training of Staff

The Clinical Investigator will ensure that appropriate training relevant to the investigation is given to the medical, nursing and other staff involved and that new information of relevance to the performance of this investigation is forwarded to the staff involved.

7.9.5 Data and Quality Management

The data collection tool for this trial will be using CRFs. Patient data necessary for analysis and reporting will be entered into a validated database or data system. Data management and handling will be conducted according to the investigation specific Data Management Plan, developed, managed and controlled by Institution.

Any deviations, i.e. discrepancies and additions from the process defined in the Data Management Plan, will be described in an investigation specific Data Management report.

7.9.6 Data Safety Monitoring Board

An independent Data Safety Monitoring Board (DSMB) will meet quarterly with the investigators and study coordinator to review study data and any major adverse events. The board will conduct interim monitoring of AEs/SAEs, oversight and analysis of study information and data to ensure the continuing safety of research participants, efficacy of the study intervention, appropriateness of the study, continued relevance of the study question, and integrity of the accumulating data throughout the life of the clinical trial. The board will be comprised of three physicians specializing in pulmonology. A summary of the DSMB findings will be submitted to the IRB with the annual renewal.

7.10 Statistical Methods and Determination of Sample Size

7.10.1 Statistical Evaluation of Performance and Safety Variables

This section provides a summary of the statistical methodology that will be used by the Institution. A more detailed description of analysis methods will be provided in a separate statistical analysis plan (SAP).

7.10.1.1 Data Sets to be Analysed

The intention to treat (ITT) population includes all randomized subjects with at least 1 verified treatment post-training during study period. The ITT population will be analyzed using the subject's randomized treatment regardless of which treatment the subject actually received.

Subjects with major protocol deviations will be excluded from the per-protocol (PP) analysis set. Subjects not taking the study treatment in the prescribed manner more than 33% of the time will be excluded from the PP analysis set. Additional subjects with exclusionary protocol deviations will be identified prior to database finalization and unblinding. Analyses for the PP will be conducted according to the randomized treatment.

All subjects entering the study will be included in the safety population. Analyses for safety population will be conducted according to the treatment actually received.

Definitions

Generally, a baseline measurement refers to the last non-missing assessment made before the first administration of study treatment (at e.g. screening and baseline).

